1. INTRODUCTION

Heart failure with preserved ejection fraction (HFpEF) is a major public health problem that is growing in prevalence, associated with poor quality of life and outcomes, and has few clearly proven treatment options.^{1,2} A major barrier to the advancement of HFpEF therapeutics is the heterogeneity of the HFpEF syndrome.³⁻⁸ It is now well recognized that a “one-size-fits-all” approach is unlikely to work in HFpEF. The heterogeneity and poor understanding of HFpEF was the rationale for the creation of dedicated HFpEF clinical programs.⁹ A number of studies over the past decade have identified specific phenotypes of HFpEF *a priori*, based upon characteristic features related to cardiac structure and function, hemodynamics, and comorbidities, with examples including obesity-related HFpEF, pulmonary vascular disease, and left atrial myopathy. In 2015, phenomapping (unsupervised machine learning) of HFpEF was first described and demonstrated both the heterogeneity of the HFpEF syndrome and the feasibility of identifying novel HFpEF subgroups via a data science approach.¹⁰ Since that initial study, several additional studies that have used machine learning to classify the HFpEF syndrome have been published.¹¹⁻¹³

In 2017, the NHLBI convened a working group on research priorities in HFpEF to address the lack of progress in identifying effective treatments in HFpEF.⁵ A key conclusion of that meeting was the need to develop a network of collaborative centers to accelerate translational and clinical research of pathobiological mechanisms underlying specific HFpEF subtypes, based on prior research in the field.¹⁴⁻²¹ The NHLBI Working Group envisioned that this resource would facilitate comprehensive, deep phenotyping of a multicenter HFpEF patient cohort with standardized protocols and a robust biorepository, which is a critical unmet need to advance subtyping of HFpEF.⁵ To address this unmet need, NHLBI released a request for applications for the HeartShare Program, which was funded in September, 2021.

Although prior studies have highlighted the heterogeneous nature of the HFpEF syndrome, additional, prospective, multi-center resources such as HeartShare are needed to advance the science of HFpEF subtyping. Identifying and understanding biologically distinct HFpEF subtypes will lead to innovative, targeted HFpEF clinical trials.²² An important unanswered question is whether prior machine learning- and omics-based subtyping of HFpEF truly represents biologically distinct subsets of HFpEF or simply subgroups based on disease progression or severity. Although both are important, the identification of biologically, mechanistically distinct HFpEF subtypes is more likely to advance HFpEF therapeutics. A multi-omics, deep phenotyping approach using both retrospective and prospective analyses, such as HeartShare, will allow us to better identify pathobiological HFpEF subtypes.

Although several studies on HFpEF phenotyping, using both conventional (e.g., pathophysiological characterization) and novel (e.g., machine learning) techniques have been published, most of these have been single center, retrospective (i.e., secondary data analyses), and/or limited in their phenotypic approach (i.e., not multi-omics).^{7,11,12} The comprehensive deep phenotyping, multi-omics approach utilized by HeartShare allows for the advancement of the scientific knowledge of HFpEF subtypes by integrating a large amount of orthogonal data over multiple centers to increase confidence in that the identified subtypes are generalizable, which will help inform future targeted HFpEF clinical trials.

Here we describe the protocol for the HeartShare Deep Phenotyping Study. This component of HeartShare is a prospective, observational, longitudinal cohort study that consists of 2 parts: (1) a HeartShare Registry, which aims to enroll up to 10,000 individuals with HF and age- and sex-matched comparators, and the HeartShare Deep Phenotyping Cohort, which aims to enroll up to 2000 participants (75% individuals with HFpEF and 25% age- and sex-matched individuals without HFpEF). Both parts of the study will enroll participants from at least 6 HeartShare

Clinical Centers. **The overall goal of the HeartShare Deep Phenotyping Study is to create a rich repository of data (e.g., demographic, social determinants of health, clinical, physiological, laboratory), images, and multi-omics (blood and tissue samples) that will serve as a resource for investigators to identify novel HFpEF subtypes and mechanisms (biological and pathophysiological) to inform future strategies for enhanced diagnosis and treatment of HFpEF.**

2. OBJECTIVES

2.1. Specific Aims

- **Overall Aim:** To establish both a HF registry and a HFpEF cohort with deep phenotyping and a biorepository to facilitate mechanistic studies and unbiased discovery approaches to HFpEF.
- **Aim 1:** To identify novel diagnostic, physiologic, imaging, and molecular markers that differentiate individuals with and without HFpEF to characterize the pathophysiology and mechanistic basis of the overall HFpEF syndrome.
- **Aim 2:** To investigate the underlying pathophysiological and biological determinants of previously identified HFpEF subtypes, including, but not limited to: (1) obesity with natriuretic peptide deficient phenotype; (2) cardiometabolic-comorbidity-inflammation phenotype; (3) myocardial-predominant phenotype; (4) left atrial myopathy phenotype; (5) supranormal ejection fraction phenotype; (6) pulmonary vascular disease, right heart failure phenotype; (7) chronotropic incompetence predominant phenotype; and (8) peripheral extraction impairment predominant phenotype.
- **Aim 3:** To identify and enable external validation of novel HFpEF subtypes using unsupervised machine learning of deep phenotyping data, images, and multi-omics, followed by further investigation to determine the underlying pathophysiological and biological determinants of these novel HFpEF subtypes.

2.2. Study Design

The HeartShare Deep Phenotyping Study is composed of 2 prospective, multicenter, longitudinal components: (1) the HeartShare Registry and (2) the HeartShare Deep Phenotyping Cohort study involving up to 10,000 and 2,000 participants, respectively, enrolled from at least 6 HeartShare Clinical Centers.

2.2.1. Organizational Structure of the Study

[figure not shown]
HeartShare is governed by a Steering Committee composed of the Principal Investigators (PIs) of the HeartShare Data Translation Center and the HeartShare Clinical Centers, NHLBI Project Scientists and Program Officers participating in HeartShare, and the Steering Committee Co-Chairs of HeartShare. The Steering Committee has the primary responsibility for the study protocol, monitoring study conduct, and reviewing data prior to reporting study results. It is also responsible for determining policies in areas such as access to participant data, ancillary studies, publications, and presentations. Study oversight is also provided by an Observational Safety and Monitoring Board (OSMB) appointed by the NHLBI. Ancillary study proposals of high scientific merit are encouraged to further enhance the scientific value of the main study and to optimize the yield from collected data, images, and biospecimens. A key aspect of HeartShare is the continuous deposit of all data, images, and omics into the NHLBI BioData Catalyst cloud computing resource so all aspects of study will be archived and shared according to NHLBI policies.

There will be several core laboratories for HeartShare, including ones for cardiopulmonary exercise testing, echocardiography, cardiac magnetic resonance imaging (MRI), arterial

stiffness/pulsatile hemodynamics assessments, pulmonary function testing, electrocardiography, tissue biopsies, multi-omics, microbiome, and clinical events. These core labs will provide central direction, personnel training, and supervision of the deep phenotyping protocol components, while supporting ascertainment of high-quality, standardized data. Study coordination, centralized data management, biospecimen management, and statistical analytic support will be provided by the HeartShare Data Translation Center at Northwestern University. All omics (i.e., genomics, proteomics, microbiome, metabolomics, epigenetics, and transcriptomics) will be conducted using the core laboratories and facilities involved in the NHLBI Trans-Omic for Precision Medicine (TOPMed).²³⁻²⁵

3. STUDY PARTICIPANTS

3.1. Participant Recruitment Methods (Figure 1)

Participants (HFpEF patients and age- and sex-matched individuals without HFpEF) for both the HeartShare Registry and the HeartShare Deep Phenotyping Cohort will be recruited at the HeartShare Clinical Centers using a variety of methods, including but not limited to: (1) a standardized electronic health record (EHR) query at each of the Clinical Centers; patients who meet the query criteria will be contacted by the study team on the phone or via electronic communication such as email or MyChart; (2) recruitment of patients who present to the Clinical Centers or clinical facilities affiliated within their health systems for evaluation of possible HFpEF, and from existing patients managed in primary care, internal medicine, cardiology, HF, and HFpEF clinics at each of the Clinical Centers; (3) outreach by the Clinical Centers to underserved populations who may not have access to healthcare at the Clinical Centers or smartphones or computers (and therefore cannot be recruited via the HeartShare Eureka app)—we will do this by specifically targeting identified HFpEF and comparator patients who reside in zip codes with lower socioeconomic status, such as the National Neighborhood Data Archive (NaNDA) and Common Ground Health; and (4) outreach by the Clinical Centers to community-based clinics and hospitals to increase the race/ethnic/socioeconomic diversity and generalizability of the HeartShare study—we will do this by giving presentations about the

HeartShare study to healthcare providers at these community-based clinics and hospitals to drive referrals for the study.

Written informed consent will be obtained from the participants by the research team prior to entry into the research study and will be performed in accordance with the guidelines and under the supervision of the Northwestern University Institutional Review Board (IRB), which will serve as the central IRB for the entire HeartShare Deep Phenotyping Study. The study procedures and the associated risks will be explained to the participants during the informed consent process. Only IRB-approved consent forms and related materials will be used for recruitment of study participants.

For the HeartShare Deep Phenotyping Cohort, our goal is to recruit a broad variety of HFpEF patients who represent HFpEF in the general population and to recruit age- and sex-matched individuals without HFpEF who have a broad spectrum of comorbidity burden ranging from healthy aged individuals to those with multiple comorbidities who do not have the HF syndrome. Age, sex, race/ethnicity, and individual comorbidities (e.g., obesity, hypertension, diabetes, chronic kidney disease, coronary artery disease, etc) will be tracked continuously in all participants of both the HeartShare Registry and the HeartShare Deep Phenotyping Cohort. The HeartShare Steering Committee, composed of PIs from the Data Translation Center and Clinical Centers and NHLBI staff, will review these metrics monthly and ensure that the enrolled participants have demographic and clinical characteristics that match epidemiological studies of HFpEF and that the comparator group has a wide range of comorbidity burden.

3.2. Inclusion/Exclusion Criteria for the HeartShare Registry

3.2.1. HF Inclusion Criteria (HeartShare Registry)

1. Age ≥ 30 years.
2. Prior diagnosis of HF in the EHR (any left ventricular ejection fraction).

3.2.2. Non-HF Group Inclusion Criteria (HeartShare Registry)

1. Age ≥ 30 years.
2. No known prior diagnosis of HF or use of loop diuretics.
3. No known prior history of BNP > 100 pg/ml or NTproBNP > 300 pg/ml, if prior laboratory tests are available in the EHR.

3.2.3. Exclusion Criteria (HeartShare Registry)

The following exclusion criteria apply to both HF and non-HF group participants, unless otherwise indicated.

1. For non-HF group: any prior known left ventricular ejection fraction $< 50\%$.
2. Prior history of solid organ transplantation.
3. Prior history of mechanical circulatory support.
4. Prior history of non-cardiac cirrhosis.
5. Inability to provide written consent to the study.

3.3. Inclusion/Exclusion Criteria for the HeartShare Deep Phenotyping Cohort

3.3.1. HFpEF Inclusion Criteria (HeartShare Deep Phenotyping Cohort)

1. Age ≥ 30 years.
2. Left ventricular ejection fraction $\geq 50\%$ measured by echocardiography.
3. Definition of HFpEF: signs and symptoms of HF, NYHA functional class II-IV, and at least one of the following:
 - a. Elevated BNP (≥ 75 pg/ml in sinus rhythm or ≥ 225 pg/ml in atrial fibrillation/flutter) or NTproBNP (≥ 225 pg/ml in sinus rhythm or ≥ 675 in atrial

fibrillation/flutter) at baseline. Choice of BNP or NTproBNP is based on availability at each clinical center.

- b. Prior HF hospitalization (primary reason for the hospitalization is HF with elevated natriuretic peptide levels [using the thresholds listed above], requiring IV diuresis for HF, or pulmonary edema or pulmonary vascular congestion on chest radiography).
- c. Elevated pulmonary capillary wedge pressure (PCWP) at rest (≥ 15 mmHg) or during exercise (≥ 25 mmHg for supine exercise or PCWP/cardiac output ratio ≥ 2 mmHg/L/min for upright exercise).
- d. Elevated H₂FPEF score²⁶ (≥ 5) or HFA-PEFF²⁷ score (≥ 5).

3.3.2. Non-HFpEF Group Inclusion Criteria (HeartShare Deep Phenotyping Cohort)

1. Age ≥ 30 years.
2. Left ventricular ejection fraction $\geq 50\%$ measured by echocardiography.
3. No known prior diagnosis of HF or use of diuretics for fluid management.
4. No known prior history of BNP ≥ 75 pg/ml or NTproBNP ≥ 225 pg/ml, if prior laboratory tests are available in the EHR.
5. BNP < 75 pg/ml or NTproBNP < 225 pg/ml at the time of screening. Choice of BNP or NTproBNP is based on availability at each clinical center.

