3.3.3. Exclusion Criteria (HeartShare Deep Phenotyping Cohort)

The following exclusion criteria apply to both HFpEF and non-HFpEF group participants, unless otherwise indicated.

1. Life expectancy estimated to be < 1 year.
2. Primary cardiomyopathy (including amyloid, hypertrophic cardiomyopathy, cardiac sarcoidosis, hemochromatosis, or other infiltrative cardiomyopathies) or pulmonary arterial hypertension (WHO Group I, III, or IV pulmonary hypertension).
3. Any prior known left ventricular ejection fraction $< 40\%$, except if this occurred only in the setting of an acute tachycardia episode (e.g., acute atrial fibrillation).
4. Clinically significant valvular heart disease defined as:
 - a. Moderate to greater aortic stenosis, pulmonic stenosis, or tricuspid stenosis.
 - b. Any mitral stenosis.
 - c. Moderate or greater aortic regurgitation.
 - d. Greater than moderate mitral regurgitation.
5. Any planned cardiac surgery or cardiac intervention in the next 3 months.
6. Alternative primary reason for symptoms of shortness of breath and exercise intolerance in HFpEF participants in the opinion of the enrolling investigator.
7. Cardiac surgery, acute coronary syndrome, percutaneous coronary intervention, stroke, transient ischemic attack, or carotid intervention in the preceding 6 months prior to enrollment.
8. Known symptomatic epicardial coronary artery disease that is not revascularized.
9. Any non-elective hospitalization in the preceding 2 weeks.
10. Prior history of solid organ transplantation.
11. Prior history of chronic infection (HIV, hepatitis C, hepatitis B, tuberculosis) unless treated and not clinically active in the opinion of the enrolling investigator.
12. Prior history of mechanical circulatory support.
13. Prior history of non-cardiac cirrhosis.
14. Estimated GFR < 20 ml/min/1.73m² or currently on dialysis.
15. Any condition that may preclude participation or adherence to the study protocol, in the opinion of the enrolling investigator.
16. Inability to provide written consent to the study.

17. Current acute decompensated heart failure.
18. Currently pregnant.
19. Uncontrolled heart rate (>110 bpm) at the time of screening.

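### The Deep Phenotyping Cohort's comparator criteria do not exclude people who meet the protocol's own HFpEF definition, so one person can qualify for both groups

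*Protocol*

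**What the plan says.** **Cases (Protocol 3.3.1, item 3).** "Definition of HFpEF: signs and symptoms of HF, NYHA functional class II-IV, and at least one of the following": (a) raised BNP or NTproBNP, (b) a prior HF hospitalization, (c) "Elevated pulmonary capillary wedge pressure (PCWP) at rest (≥ 15 mmHg) or during exercise", (d) "Elevated H₂FPEF score²⁶ (≥ 5) or HFA-PEFF²⁷ score (≥ 5". Any one is enough. Routes (c) and (d) do not carry a prior diagnosis or a raised natriuretic peptide as a separate requirement.

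**Comparators (Protocol 3.3.2).** There are five criteria: age of at least 30; LVEF of at least 50% on echocardiography; "No known prior diagnosis of HF or use of diuretics for fluid management"; no known earlier BNP of 75 pg/ml or more or NTproBNP of 225 pg/ml or more, where results exist in the EHR; and "BNP < 75 pg/ml or NTproBNP < 225 pg/ml at the time of screening".

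**Intent (Protocol 3.1).** Comparators are to range from healthy older people to "those with multiple comorbidities who do not have the HF syndrome".

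**Prior LVEF.** The Registry has an exclusion, "For non-HF group: any prior known left ventricular ejection fraction", set at below 50% (3.2.3). The cohort's exclusion, "Any prior known left ventricular ejection fraction", is set at below 40% and applies to both groups, with an exception for acute tachycardia (3.3.3, item 3).

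**The concern.** Aim 1 is the contrast between people with and without HFpEF, and it depends on the comparator group being free of the condition. Section 3.3.2 checks what is already known about a person (diagnosis, fluid diuretic, earlier peptide values) and one screening laboratory value. It does not check whether the person has the syndrome as 3.3.1 defines it, and no rule says where to place someone who fits both groups.

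The recruitment plan makes such people reachable. Section 3.1 recruits both groups by routes that include patients presenting for evaluation of possible HFpEF, and it deliberately seeks comparators with several comorbidities.

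If cases enter the comparator group, Aim 1 differences would tend to be understated. Enrolling more people improves precision but does not remove that bias.

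**Working it through.** **1. Do the two definitions overlap?** Take current LVEF of at least 50%, signs and symptoms, and NYHA II-IV as given, and test each case route against 3.3.2.

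| Route in 3.3.1 item 3 | Closed by 3.3.2? |
|---|---|
| (a) raised BNP/NTproBNP at baseline | Yes, if the same value is used: screening BNP must be below 75 or NTproBNP below 225 |
| (b) prior HF hospitalization | Yes, in effect: it implies a known HF diagnosis |
| (c) raised PCWP | No |
| (d) H2FPEF or HFA-PEFF score of at least 5 | No |

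Enumerating combinations of symptoms, screening BNP, rhythm, prior diagnosis, diuretic use, prior BNP, hospitalization, PCWP and score gives the same result. Profiles that meet both sets exist only through (c), (d) or both, in sinus rhythm or atrial fibrillation.

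**2. Do the shared exclusions in 3.3.3 close the gap?** No. Item 17 covers only current acute decompensation. Item 6 (another primary reason for symptoms) is limited to HFpEF participants. Nothing else in the list concerns symptoms, NYHA class, score or PCWP.

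**3. Reproduce the plan's figure.** Inputs from 6.2, Table 3a: 750 HFpEF, 250 comparators, two-sided alpha 0.0005, 80% power, printed standardized difference 0.316.

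- Standard error = √(1/750 + 1/250) = 0.07303.
- Normal approximation: (3.481 + 0.842) × 0.07303 = 0.3157. The noncentral t gives 0.3166. The printed 0.316 is reproduced.
- Noncentral t power at 0.316 is 0.798, that is 80%.

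**4. Effect of contamination (m is assumed; the protocol gives none).** If a share m of comparators have the average HFpEF value of a marker, the comparator mean moves by m·d, and the observed difference is d(1 − m). Power is by noncentral t. The true difference needed for 80% power is 0.3166/(1 − m).

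| m | Observed difference | Power, 750 v 250 | True difference needed for 80%, 750 v 250 | Power, 1500 v 500 |
|---|---|---|---|---|
| 0 | 0.316 | 80% | 0.317 | >99% |
| 5% | 0.300 | 73% | 0.333 | 99% |
| 10% | 0.284 | 66% | 0.352 | 98% |
| 20% | 0.253 | 49% | 0.396 | 92% |

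Check of the last cell by normal approximation: 0.2528 × √375 − 3.481 = 1.41, which corresponds to 92%. Letting the comparator SD widen because the group is a mixture changes little (at m = 20% and 750 v 250, normal approximation, 0.484 instead of 0.492).

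**The case against.** **Intent and name.** The group is called non-HFpEF, and 3.1 says its members do not have the syndrome, so an investigator who recognises HFpEF would be expected not to enrol that person as a comparator. This may lower contamination in practice. It is not an eligibility criterion, however, and it does not reach the person whose HFpEF nobody has yet looked for.

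**Size.** No figure in the protocol supports any value of m. The factor (1 − m) also assumes that misclassified comparators resemble average HFpEF cases. By selection they have low natriuretic peptides, no fluid diuretic and no known diagnosis, so attenuation will differ by marker. A reader might infer that every difference shrinks by the same factor, but the documents do not support that; screening BNP, for example, is capped for all comparators. The table uses the minimum of 1000 participants, while 6.1 allows up to 2000. All of this stands and limits what the numbers can show.

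**Aim 2.** Because the overlap concerns people with low natriuretic peptides, a reader might infer damage to the first Aim 2 subtype, obesity with natriuretic peptide deficiency. Section 6.3 compares each subtype with all other HFpEF patients. Comparators enter only in the follow-up bioinformatics step, so the main Aim 2 contrast is unaffected.

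**Prior LVEF.** A reader might infer that admitting comparators with a past LVEF of 40-49% also lets cases in. It does not by itself: someone with current LVEF of at least 50% and no symptoms fails 3.3.1. The Registry's non-HF group serves a different case definition (HF at any LVEF), so the different limit is not a contradiction. The text does not say whether cohort comparators must first qualify for the Registry's non-HF group, and Figure 1 is not available here.

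**Recoverability.** All participants undergo the same phenotyping (5.2), so many overlaps can be identified later. This also stands, and it makes the problem cheap to correct.

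**Conclusion.** The overlap is established from the text alone and needs no assumption: routes (c) and (d) of the HFpEF definition remain open to someone who satisfies every comparator criterion. Eligibility is fixed in the protocol, so this is not a detail for a later analysis plan. The likely direction is bias of Aim 1 contrasts toward the null.

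The amount is unknown. At 750 v 250, alpha 0.0005 and a true difference of 0.316, power would be 73%, 66% and 49% for assumed m of 5%, 10% and 20%, provided that misclassified comparators look like average cases. At 1500 v 500 it would still be 92% at m = 20%. The printed Table 3a is arithmetically sound and holds as stated when m = 0.

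The difference in prior-LVEF limits is a minor, separate matter of consistency.

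**What to change.** 1. Add to 3.3.2 a criterion that the person does not meet the HFpEF definition in 3.3.1 item 3, judged as far as available data allow and with no added invasive testing. Because item 3 also requires symptoms and NYHA II-IV, asymptomatic people with many comorbidities remain eligible, and the comorbidity range sought in 3.1 is kept.
2. For comparators already enrolled, flag those who meet the definition on baseline symptoms, NYHA class, echocardiography and laboratory data. Leave them out of the Aim 1 comparator set, at least as a sensitivity analysis. The protocol does not list the components of the two scores, so the study team should first confirm that both can be computed from the data collected.
3. Separately, reconcile the prior-LVEF limits for comparators in 3.2.3 and 3.3.3, or state why they differ.

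The cost is one protocol amendment, a derived flag, and probably a small loss of comparators, which continuing recruitment can replace.
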